### Introduction to the Objective and Rationale of the Trial

In the past 5 years, there is a growing number of published articles showing the suitability and benefits of the use of high frequency oscillation (HFO) in patients with acute respiratory distress syndrome (ARDS) (1-4). In 2002, Derdak and associates published the results of a randomized controlled trial comparing HFO and conventional mechanical ventilation (CMV) in patients with ARDS. The CMV group did not receive lung protective CMV (1). There was a trend toward a significant decrease in 30-day mortality in the HFO group (37% vs. 52% in the CMV group, P=0.102). The HFO group mortality was comparable to the mortality reported by the ARDSnet trial published in the year 2000; in this trial, patients received low tidal volume CMV (5). It should be noted that Derdak et al employed "moderate" tidal volumes (6-9), the use of which was subsequently supported by the results of the meta-analysis of Eichacker et al (10). However, as Levy points out (11), the mortality of 26-31% in a total of 1000 patients treated with low tidal volumes [if one combines the data of the 2 ARDSnet studies (5,12)] indicates that the open lung-low tidal volume ventilation is the most effective CMV strategy in ARDS.

During HFO, the proposed mechanisms of gas-exchange include 1) bulk convection, 2) pendelluft effect, 3) asymmetric velocity profiles, 4) Taylor dispersion and turbulence, 5) cardiogenic mixing, 6) molecular diffusion, and 7) collateral ventilation (13).

Tracheal gas insufflation (TGI) constitutes an interesting adjunct to CMV for patients with severe ARDS. Conventional forward thrust TGI improves  $CO_2$  elimination (14). Two theories have been developed, in order to explain the efficacy of TGI (14-16). The first theory proposes the washout of the anatomic deadspace, and the second theory supports the augmentation of alveolar ventilation. The removal of  $CO_2$  – rich gas from the anatomic deadspace and its  $O_2$  – rich and  $CO_2$  – free gas prevents the reentry of  $CO_2$  into the alveoli during the subsequent inspiration (deadspace washout mechanism). Alveolar ventilation may also be augmented by 1) the increase in the mixing of the gases distally to the central airways due to the high-velocity and probably turbulent TGI flow, and 2) the enhancement of collateral ventilation.

In our preceding study (paper submitted to Crit Care Med), we showed that the combination of HFO with TGI (HFO-TGI) improves gas-exchange as compared to lung protective CMV. In the present study, we intend to determine the effect of HFO-TGI on the survival of patients with severe ARDS. Our main hypotheses are that 1) HFO-TGI will improve oxygenation and lung recruitment, thus resulting in reduced ventilation pressures during the subsequent CMV, and 2) this reduction in the injurious mechanical stresses to the lung may attenuate ventilator-associated lung injury and thus improve survival. This is also the major proposed mechanism of survival improvement by low-stretch, low-volume CMV (5).

**METHODS** 

**Patients** 

Study participants must fulfill the following eligibility criteria: 1) early ARDS (establishment of the diagnosis within the preceding 72 hours) according to the criteria of the American-European Consensus Conference (18), 2) severe oxygen disturbance [defined as ratio of partial pressure of arterial oxygen (PaO2) to inspired oxygen fraction (FiO2)<150mmHg, while they are on CMV with positive endexpiratory pressure (PEEP) set at ≥8cmH2O, 3) age 18-75 years, body weight >40 Kg, and 4) absence of a) severe air leak (more than one chest tubes per hemithorax with persistent air leak for more than 72 hours), b) systolic blood pressure lower than 90 mmHg, despite maximum support with fluids and vasopressor drugs (i.e., norepinephrine infusion rate exceeding 0,5 µg/kg/min, c) significant heart disease (e.g. ejection fraction lower than 40%, history of pulmonary edema and active ischemic disease or myocardial infarction), d) severe chronic obstructive pulmonary disease (COPD) or asthma (e.g. previous admission for COPD/asthma, chronic treatment with corticosteroids for COPD/asthma, and chronic CO2 retention more than 50 mmHg), e) intracranial pathology with intracranial pressure >20mmHg, not responsive to conservative treatment (e.g. hemorrhage, head injury, tumor, infection or acute ischemic stroke), f) chronic interstitial lung disease with bilateral lung infiltrates, g) lung biopsy or incision during the current admission, h) previous lung transplantation or bone marrow transplantation, i) pregnancy, j) immunosuppression, and k) participation in another clinical study.

2

Randomization will result in assignment to either the control group (treatment with CMV) or the HFO-TGI group (treatment with CMV and HFO-TGI sessions, as described in the following paragraphs). The randomization technique will comprise the use of computer-generated sequence(s) of random numbers and a "sealed envelope technique", in order to achieve concealment until patient study entry.

Continuous monitoring of patients will include electrocardiographic lead II, intraarterial pressure [and/or cardiac index (PICCO plus, Pulsion Medical Systems, Munich, Germany)] and peripheral oxygen saturation (SpO2). Maintenance of anesthesia will be achieved with intravenous midazolam or propofol and/or fentanyl or remifentanyl. Neuromuscular blockade (cisatracurium) will be used in concordance with recent recommendations (19), and/or as part of the treatment prescribed by the attending physicians. The sedation protocol is illustrated in Figure 1, and reflects mainly our standard clinical practice.

# **Conventional Mechanical Ventilation Strategy**

Patients eligible for the study will be initially on CMV ([Siemens 300C ventilator (Siemens, Berlin, Germany), or Galileo Gold ventilator (Hamilton Medical, Bonaduz, Switzerland)] with the following FiO2/PEEP combinations: 0.6/10 cm H2O, 0.7/10-14 cm H2O, 0.8/14 cm H2O, 0.9/16 cm H2O, 1.0/16-20 cm H2O. The tidal volume will be 5.5-7.5ml/kg predicted body weight with a maximum plateau pressure of 35 cmH2O. The goals for tidal volume and plateau pressure will be 6.0 ml/Kg predicted body weight and 30 cmH2O, respectively, provided that the below-mentioned gas exchange goals are achievable. Respiratory rate will be adjusted so that arterial pH (pHa) will be maintained from 7.20-7.30 to 7.45 and the inspiratory to expiratory time (I/E) ratio will be 1:2. Oxygenation targets will be as follows: SaO2=90-95% or PaO2=60-80 mmHg. The target pHa will be >7.20. Recruitment maneuvers (RM) [continuous-positive airway pressure of 45 cmH2O (40-50) for 20-40 sec depending on patient tolerance] will be performed every 4-6 hours for the first 4 days after randomization in the control group. The CMV strategy is summarized in Table 1.

# HFO-TGI strategy-main study intervention protocol

Recently published recommendations regarding HFO use (Sensormedics 3100B ventilator, Sensormedics, Yorba Linda, CA, USA) include the following steps (20).

- 1) Sufficient level of sedation for the abolishment of respiratory muscles activity, with or without neuromuscular blockade, so that patient-ventilator dyssynchrony is avoided (21-24).
- 2) Confirmation of endotracheal tube patency and placement of the tube at 3-4 cm above carina.
- 3) RMs: immediately after patient-oscillator connection, an RM will be performed [increase in the circuit pressure to 45 (40-50) cmH2O for 20-40 sec depending on patient tolerance, with the oscillator's piston off]. RMs will be repeated every 2-12 hours approximately.
- 4)  $FiO_2$  will initially be set at 1.0.
- 5) Bias flow will be set at 30-40 L/min.
- 6) According to the data of our preceding study (paper submitted to Crit Care Med), TGI will be equal to 50% of the preceding CMV minute ventilation; this is also consistent with an earlier study of our group (25).
- 7) Initial oscillation frequency will be 4 Hz, and will be titrated according to pHa>7.20-7.30, with a minimum value of 3 Hz. Oscillatory pressure amplitude ( $\Delta P$ ) will be set within 60-100 cmH2O and will be titrated according to pHa>7.20-7.30.
- 8) A tracheal tube cuff leak will be placed to facilitate CO2 elimination. The associated reduction in mean airway pressure (mPaw) of 3-5 cmH2O will be immediately reversed by using the corresponding control knob.
- 9) I:E ratio will be maintained at 1:2.
- 10) Initial adjustments and the subsequent de-escalation of mPaw (and TGI will be conducted as follows: A] Initial mPaw = mPaw CMV + 8-10 cm H2O (depending on CMV tracheal pressure), or approximate equivalent, i.e. mPaw = 2-3 cmH2O above the point of maximal curvature of the expiratory pressure-volume curve (if the curve is constructed) B] mPaw reduction by 1-2 cmH2O every 1-2 hours, with a final target to reduce initial mPaw by 6 cmH2O and maintain a PaO2/FiO2 of >150 mmHg, C] discontinuation of TGI over 30 min, and reconfirmation that PaO2/FiO2 remains at >150 mmHg after another 30 min, D] return to CMV. The main indication for return to HFO-TGI will be a PaO2/FiO2 of <150 mmHg with PEEP ≥ 8 cmH2O for > 12 hours. The minimum total time of HFO-TGI will be 12 hours.

A study protocol schema is provided in Figure 2, whereas the proposed intervention failure algorithm is illustrated in Figure 3. The HFO-TGI protocol will be based on the simple principle of "Recruit – Stabilize – and Wean, and Rerecruit if necessary". The minimum duration of the recruitment period will be 60 min; the minimum duration of the stabilization period will be 4 hours; the minimum duration of the weaning period will be 60 min; and the minimum duration of the HFO-TGI session will be 6 hours. HFO-TGI sessions will be extended according to the need of use of the Additional Recruitment Algorithm. The maximum duration of application of the HFO-TGI intervention will be 10 days.

### **Patient Safety Features**

The lowest allowable  $SpO_2$  will be 88% for the whole duration of the HFO-TGI protocol. An  $SpO_2$  of <88% for  $\geq 5$  min will trigger immediate transition to the Additional Recruitment Algorithm [and/or its subsequent step(s) if still persisting for

another 5 min (Figure 2)]. During HFO-TGI sessions, the maximum set mPaw will never exceed 40 cmH2O (allowance may be made up to 45 cmH2O for the case of intervention failure). In addition, systolic blood pressure value will be maintained at >90 mmHg, mean blood pressure will be maintained at >60 mmHg, and reductions in cardiac output/index of >10% will be treated with fluids and vasopressors. RMs resulting in any of the immediately aforementioned hemodynamic perturbations will be aborted and withheld for 12 hours; the same action will be undertaken if RMs result in desaturation (i.e., SpO2 <85% or absolute SPO2 decrease of >5%). At the end of the HFO-TGI sessions, a brief fiberoptic inspection of the trachea will be carried out (by a study-independent physician), in order to exclude or confirm the presence of TGI-related mucosal damage; the proposed grading of endoscopic findings is presented in Table 2; TGI-related mucosal damage in a patient will result in discontinuation of TGI use in that particular patient. Lastly, during HFO-TGI and in the presence of a tracheal tube cuff leak, the nasogastric tube will be placed on drainage to minimize any potential risk of aspiration of gastric contents.

# Weaning from CMV

The corresponding proposed protocol is presented in Figure 4.

### **Patient Follow-up**

Data on demographic, physiologic, and radiographic characteristics, coexisting conditions, and medication will be recorded within 4 hours prior to randomization. For the first 10 days post-randomization, at least 3 sets physiologic measurements (blood-gas analysis, hemodynamics, and respiratory mechanics during CMV) will be obtained daily. Laboratory, radiographic/imaging (with special emphasis on barotrauma; assessments to be carried out by study-independent radiologists), and physiologic data will be collected daily until weaning from CMV and/or intensive care unit (ICU) discharge or death. Patients will be monitored daily for signs of failure of nonpulmonary organs and systems. Patient clinical course will be documented until hospital discharge or death.

### **Outcome Measures**

### **Primary:**

• Survival to days 28 and 60 post-randomization, and to Hospital Discharge (patient discharged home while breathing without assistance).

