### **Power Analysis and Study Periods**

Based on pilot data, we estimate an absolute HFO-TGI related improvement of 26% in the survival to hospital discharge. For the determination of a 26% absolute difference in hospital mortality with alpha=0.05 and power=0.80, a total sample size of 124 patients will be required.

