# First study period planning

An interim analysis assessing safety data will be conducted after the enrolment of 20 patients. Following the (probable in our opinion) establishment of patient safety, we will be able to extend the study until the enrolment and follow-up completion of 50-54 patients. Based on our pilot period data, we have estimated an HFO-TGI-related improvement in compliance of 25% within days 5-10 (improvement most likely to be confirmed within days 5-8). For alpha = 0.05 and power = 0.80, we will have to enroll 52 patients, whereas the enrollment of 54 patients will raise power to 0.82." Consequently, provided that our pilot data-based prediction is confirmed in the first 20 participants of the first study period, we will conclude that this study period will be adequately powered to assess the evolution of respiratory physiology during

[figure not shown]
the study intervention period. As according to our original hypothesis the evolution of respiratory physiology is a prerequisite for an HFO-TGI-associated improvement in survival, following the aforementioned confirmation, we will add this "intermediate" outcome to the (registered with Clinicaltrials.gov) primary outcome measures of the first study period.

The other primary outcome measure for the first study period will be (as for the whole study) survival to hospital discharge; additional survival assessment time points may include days 28 and 60 post-randomization. The current study period will not be sufficiently powered to reliable assess in-hospital mortality. Nevertheless, regarding 28-day survival, a possible, large chi-square effect size of 0.5-0.6 would result in alpha ≤0.04 and power ≥0.81. This will correspond to a between-group, 28-day survival difference similar to that determined in the Amato trial [i.e. 34% (26)]. However, in such a case, a large difference in 28-day survival will also likely be reflected by a concurrent difference in ventilator-free days (26), which in turn will be explained by early improvements in the respiratory physiology of the HFO-TGI group. Regarding the potential for TGI-associated tracheal mucosal damage (14), this will be assessed as feasible (feasibility to be confirmed during the first period) according to the pre-specified grading of Table 2.

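### The protocol gives two answers on which survival outcome is primary, and two non-equivalent definitions of the hospital outcome on which the 124 patients rest

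*Protocol*

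**What the plan says.** Three places in the Protocol bear on the primary outcome.

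- **Outcome Measures, Primary.** One bullet: "Survival to days 28 and 60 post-randomization, and to Hospital Discharge (patient discharged home while breathing without assistance". Three time points stand side by side. None is named as leading, and the parenthesis restricts the hospital outcome by destination and by breathing support.
- **Power Analysis and Study Periods.** The planning effect is "an absolute HFO-TGI related improvement of 26% in the survival to hospital discharge". The next sentence sizes the trial for a "26% absolute difference in hospital mortality with alpha=0.05 and power=0.80", and concludes that "a total sample size of 124 patients will be required". No control-arm rate is given, and days 28 and 60 are not mentioned.
- **First study period planning.** Survival to hospital discharge is named as a primary measure of the first period, with a parenthesis saying that this is also so for the whole study. The sentence goes on: "additional survival assessment time points may include days 28 and 60 post-randomization".

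**The concern.** Two separate inconsistencies are in the Protocol itself.

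First, the outcome list makes days 28 and 60 co-equal primaries, whereas the first-period plan gives the whole-study primary as the hospital outcome and speaks of the other two as additions that may be made. A reader who follows one section could report a different primary result from a reader who follows the other.

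Second, the power section moves from survival to hospital discharge to hospital mortality as if each were one minus the other. Under the outcome list's parenthesis they are not complements. Patients transferred alive to another facility, or leaving with breathing support, fall between the two. The notes to Figure 4 provide for tracheostomy and for return to ventilation after failed spontaneous breathing, so such discharges are conceivable, although the Protocol gives no frequency. This problem would remain even if the hospital outcome were the only primary.

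At stake are which result counts as the trial's answer, and whether the 124 patients give the intended power for the outcome as defined.

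**Working it through.** **1. The plan's own figure.** Inputs from Power Analysis and Study Periods: difference d = 0.26, alpha 0.05, power 0.80, total 124. Not given: the control rate, the number of sides, and the allocation ratio (the Patients section says only "Randomization will result in assignment to either the control group (treatment with CMV) or the HFO-TGI group"). I assume two-sided testing and 1:1 allocation, so 62 per arm. With p̄ the mean of the two rates, the number per arm is

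n = [1.960·√(2p̄(1−p̄)) + 0.8416·√(p1(1−p1) + p2(1−p2))]² / d².

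For survival of 26% against 52%, p̄ = 0.39 and n = (1.960 × 0.6898 + 0.8416 × 0.6648)² / 0.0676 = 54.05, so 55 per arm and 110 in total. The continuity correction, n′ = (n/4)·[1 + √(1 + 4/(n·d))]², gives 61.5, so 62 per arm and 124 in total. The corrected formula also gives 124 at 47% against 73%. Over control survival from 20% to 71%, the uncorrected formula never exceeds 114. So 124 cannot be confirmed without a control rate, but it is attainable and is not shown to be wrong.

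**2. The sections side by side.**

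| Section | Days 28 and 60 | Hospital outcome |
|---|---|---|
| Outcome Measures, Primary | primary | primary; home and unassisted |
| Power Analysis and Study Periods | not mentioned | basis of 124; used as complement of hospital mortality |
| First study period planning | possible additions (sentence about the first period) | primary for that period and for the whole study |

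Rows 1 and 3 disagree on the status of days 28 and 60. Rows 1 and 2 disagree on what the hospital outcome is.

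**3. What the definition gap could cost.** Let f be the share of hospital survivors not discharged home unassisted, equal in both arms (assumption). Rates p1 and p2 become p1(1−f) and p2(1−f), so the difference becomes 26(1−f) points: 23.4 at f = 10% and 20.8 at f = 20%. Power is Φ[(d − 1.960·se0)/se1], where se0 = √(2p̄(1−p̄)/62) and se1 = √((p1(1−p1) + p2(1−p2))/62), without continuity correction.

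Example with assumed control survival 37%:
- f = 0: 37% against 63%; (0.26 − 1.960 × 0.0898)/0.0867 = 0.97; power 83%.
- f = 10%: 33.3% against 56.7%; (0.234 − 1.960 × 0.0894)/0.0868 = 0.68; power 75%.

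Over control survival of 30-45%, power is 83-84% at f = 0, 75-77% at f = 10% and 64-69% at f = 20%.

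**4. What an any-of-three rule would do.** I simulated null trials of 62 per arm with nested deaths (day 28 within day 60 within hospital). Assumed mortality was 30-45% at day 28, 45-55% at day 60 and 50-60% in hospital. Each outcome was tested at 0.05, 200,000 trials per scenario.

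| Rule | Test | False-positive rate |
|---|---|---|
| Hospital mortality alone | uncorrected chi-square | 5.4-6.0% |
| Any of three | uncorrected chi-square | 9.9-11.9% |
| Any of three | continuity-corrected | 6.6-7.9% |
| All three | uncorrected chi-square | at most 2.4% |

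**The case against.** The strongest reply is that a lead outcome can be found. The first-period plan names survival to hospital discharge for the whole study, and the sample size rests on it. That stands: the fault is a contradiction between sections, and it would go too far to infer that the Protocol leaves success undefined. The remark on days 28 and 60 also sits in a sentence about the first period, so it does not by itself make them optional for the whole trial. The outcome list still contradicts the whole-study parenthesis.

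A reader might infer that the trial runs a 10-12% false-positive rate. The documents do not support this. No section says that any one of the three suffices, the list joins them with the word and, and a multiplicity rule could sit in an SAP that is not shown. The figure is conditional on that rule, on an uncorrected test and on assumed mortality. Since 124 is reached in step 1 only with a continuity correction, the 7-8% figure is at least as relevant.

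A reader might also infer that the trial was sized for the wrong outcome. The power section uses both terms as synonyms, so it does not choose mortality against the outcome list. It overlooks that the list's definition separates them. One could read the parenthesis as only stating when discharge counts as having occurred, but the Protocol does not say so.

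Two further inferences fail. Applying a 5-10% rate of other discharges to all 124 patients would suggest 6-12 reclassified. Only patients discharged alive can be reclassified: at 50-60% hospital mortality that is 50-62 patients, so about 2-6. And no section says who decides discharge or destination, so a claim that unblinded staff decide the endpoint is inference.

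Finally, it may be said that day 28 is powered too. The first-period plan's remark is conditional on a chi-square effect size of 0.5-0.6. The 34-point difference it cites corresponds to d/(2√(p̄(1−p̄))), about 0.34-0.37, and to about 70-72% power with 26-27 per arm at alpha 0.05. It does not make day 28 a powered primary for the trial.

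**Conclusion.** The concern holds as a contradiction inside the Protocol, not as a detail that an SAP may supply. The status of days 28 and 60 differs between the outcome list and the first-period plan, and the hospital outcome has two definitions that classify some living patients differently. No error in the 124 is shown.

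The clearest consequence is the definition gap: with 10% of survivors in each arm not going home unassisted, 26 points become 23.4 and power falls from about 84% to about 75-77%. This rests on the assumed share, on its being equal in the arms, on control survival of 30-45%, on 1:1 two-sided testing and on no continuity correction. The inflation of the false-positive rate (about 10-12% uncorrected, about 7-8% corrected) arises only under an any-of-three rule that the Protocol neither states nor excludes. This should be fixed; it does not undermine the design.

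**What to change.** In Outcome Measures, name one primary, survival to hospital discharge, and move survival to days 28 and 60 to the secondary outcomes. This agrees with the sample-size basis and with the whole-study statement in the first-period plan.

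Then use one definition in all three sections. The preferred choice is alive at hospital discharge, because it is the complement of the hospital mortality for which the 124 patients were calculated; discharge home and unassisted becomes a secondary outcome. No section says that destination is to be ignored, so this is a choice that aligns the definition with the quantity that was sized, and it should be presented as such. State the control rate behind 124 at the same time.

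If the outcome list's definition is kept, restate the sample-size basis for that outcome. As an illustration with the uncorrected formula of step 1, 33.3% against 56.7% gives (1.960 × 0.7036 + 0.8416 × 0.6838)² / 0.234² = 69.8, so 70 per arm and 140 in total, against 114 for 37% against 63%.

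Cost under the preferred definition: wording changes, and days 28 and 60 lose primary status. N stays 124 and no further data are needed.
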